## Proposal Narrative

### **I. Hypotheses and Specific Aims:**

#### Specific Aim:

- To evaluate the pharmacokinetic effect of rifampin on serum etonogestrel concentrations in contraceptive implant users at the dose of rifampin used for latent tuberculosis infection (LTBI) treatment (600mg per day)
- Exploratory Aim – to evaluate the effect of rifampin on serologic measures of ovulatory suppression (estradiol and progesterone) in contraceptive implant users

#### Hypothesis:

- We hypothesize that rifampin will have a significant pharmacokinetic effect on participants' etonogestrel levels resulting in etonogestrel concentrations at least 35% decreased from baseline measurements.

### **II. Background and Significance:**

Rifampin is an antibiotic historically prescribed as part of a treatment regimen for active tuberculosis (TB) infection. Though active TB infections have become rarer over time in the US, it is estimated that up to 13 million people in the US may have latent TB infections (LTBIs), with even greater numbers of LTBIs worldwide. In efforts to combat the persistent rate of LTBI, the US Centers for Disease Control and Prevention (CDC) released updated treatment guidelines for LTBI in 2018. This recommended treatment guideline consists of four treatment regimens, varying in duration from 3 to 9 months. The CDC recommends utilization of the shorter regimens when possible to achieve higher patient compliance and infection clear rates. The second shortest duration treatment regimen (4 months) consists of daily rifampin only.

In addition to its antitubercular properties, rifampin is a known strong cytochrome P-450 (CYP) 3A4 enzyme inducer. Similar to other strong CYP3A4 enzyme inducers (e.g. carbamazepine), rifampin can affect the serum concentrations of exogenous steroid hormones found in hormonal contraception. The only published literature on the interaction between rifampin and hormonal contraception has focused on combined oral contraceptives. Five studies that investigated the pharmacokinetics of combined oral contraceptives all found significant reductions in serum ethinyl estradiol and progestin concentrations with rifampin co-administration. This pharmacokinetic effect is significant enough to warrant a category 3 recommendation (theoretical or proven risks usually outweigh the advantages) from the CDC Medical Eligibility Criteria (MEC) for Contraceptive Use for concomitant rifampin and combined hormonal contraceptive methods. This pharmacokinetic effect is large enough to raise concerns for combined hormonal contraceptive method efficacy and recommendation of alternative methods. One of those alternative methods is the etonogestrel (ENG) implant (Nexplanon®), which has a category 2 recommendation in the CDC MEC for concomitant rifampin use. However, in

the clarifications for this recommendation, the CDC MEC warns that rifampin is “likely to reduce the effectiveness” of the ENG implant, with no supporting evidence provided.

#### **IV. Research Methods**

##### **A. Outcome Measure(s):**

###### Primary outcome:

- Serum etonogestrel concentrations measured before and after concomitant rifampin therapy

###### Secondary outcomes:

- Serum estradiol (E2) and serum progesteron (P4) concentrations measured before and after concomitant rifampin therapy

##### **B. Description of Population to be Enrolled:**

We aim to enroll up to 15 reproductive age (18-45 years) women in this study based on the following criteria:

- Inclusion Criteria: Healthy women, who have had an ENG implant for 12-36 months at the time of enrollment and will maintain their implant during the study without modifications.
- Exclusion Criteria (at baseline):
  - We will exclude women who are taking any known cytochrome P-450 3A4 enzyme inducers or inhibitors.
  - We will exclude women with a known allergy or insensitivity to rifampin.

- We will also exclude women with a body mass index (BMI) <18.5, as underweight women may have altered metabolism. We will not have an upper BMI cut-off as studies have shown that overweight and obese women have equivalent metabolism and efficacy with the ENG contraceptive implant.
- Exclusions Criteria (screening laboratory testing)
  - We will also exclude women with any hepatic or renal dysfunction as determined by a comprehensive metabolic panel. For purposes of this study, liver function tests will be evaluated and evidence of hepatic dysfunction will be defined as an ALT >52 or AST >39, which are beyond the reference range of normal values used by the University of Colorado clinical laboratory. Renal function will be assessed by a serum creatinine and a value >1.2 will be evidence of renal dysfunction as this is greater than the reference range used by the University of Colorado clinical laboratory.
  - We will also exclude women with any abnormal hematology as determined by a complete blood count. For purposes of this study, abnormal hematology will be defined as a WBC, RBC, or PLT value beyond the reference range of normal values used by the University of Colorado clinical laboratory.
  - We will also exclude women with abnormal coagulation factors as determined by coagulation factor tests (PT/INR, PTT). For purposes of this study, abnormal coagulation factors will be defined as any test value beyond the reference range of normal values used by the University of Colorado clinical laboratory.

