### **C. Study Design and Research Methods**

We propose a prospective, pre and post study to evaluate the pharmacokinetic effect of rifampin on serum ENG levels in contraceptive implant users. We will enroll healthy women using an ENG implant for at least 12 months and no greater than 36 months. Our exclusion and inclusion criteria are detailed as above. Interested participants will undergo a phone screening prior to scheduling an enrollment visit. At the enrollment visit, potential participants will have their vital signs checked in the form of a pulse and blood pressure and will have their height and weight measured for purposes of calculating a body mass index. We will review each potential participants past medical history and current medications to ensure study eligibility. If interested participants meet our non-laboratory inclusion and exclusion criteria, then they will undergo informed consent in a private clinic room.

After the participant has been consented, we will perform a blood draw to obtain whole blood and serum. Appropriate blood samples will be sent to the University of Colorado Clinical Laboratory for a comprehensive metabolic panel, complete blood count, and coagulation factor testing (PT/INR, PTT). We will also obtain additional blood tubes for measurement of serum estradiol and progesterone. These tubes will be sent to the UCH Clinical Laboratory for analysis if the participant's screening laboratory testing is normal. A blood sample for serum will be centrifuged on location and the serum collected for

storage in our -80°F freezer. For participants that meet our laboratory exclusion criteria, we will ultimately measure a serum baseline ENG concentration from the serum collected at the enrollment visit. The research team will then follow-up the screening laboratory tests to determine final eligibility based on the criteria discussed above. Eligible participants will then be given the options of either returning to our clinic to pick up the study medication or have the study medication mailed to them via FedEx.

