#### **F. Data Analysis Plan:**

For this study, we aim to show a decrease in serum ENG concentrations of at least 35% from baseline, which would be consistent with the effect of a moderate to strong CYP3A4 inducer based on FDA standard definitions. Based on our previous cohort of 350 ENG implant users, we converted the median and range of serum ENG from that cohort to a mean of 137.4pg/mL with a SD of 106.6 based on Hozo et al's (BMC Med Res Methodol, 2005) formula. We then determined the assumed standard deviation of the differences in serum ENG concentrations to be 53.3 for before and after rifampin exposure based on an assumed correlation of 0.875 between these measurements. In order to find at least a 35% decrease in serum ENG concentrations (at least 48.1pg/mL decrease) with alpha level of 0.05 and power of 0.9, we will need 13 study compliant participants. Given the non-normal distribution of serum ENG concentrations, we will plan for 15 study compliant participants. We expect the discontinuation rate to be low given the short period

of treatment time (2 weeks), and so will plan for enrollment of 15 participants. If our discontinuation rate is higher than expected, then we will consider additional enrollment as needed.

We will use a paired Wilcoxon signed rank test to compare pre and post exposure serum ENG concentrations with each participant serving as their own control. We use the same analytic test for comparing pre and post exposure estradiol and progesterone levels. We will use a p-value of <0.05 as a cut-off for statistical significance. As each participant serves as her own control, we do not need to incorporate demographic factors into our analyses.

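### The plan enrols 15 women to obtain 15 compliant women, leaves what the 15 counts undefined, and has no real power reserve for losses

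*Combined protocol and SAP*

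**What the plan says.** Three statements about numbers have to be read together.

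- Section IV.B (Description of Population to be Enrolled) gives a maximum: "We aim to enroll up to 15 reproductive age (18-45 years) women". The criteria that follow include the screening laboratory exclusions.
- Section F (Data Analysis Plan) says "we will need 13 study compliant participants" for a 35% decrease at alpha 0.05 and power 0.9. It continues: "Given the non-normal distribution of serum ENG concentrations, we will plan for 15 study compliant participants". It expects little discontinuation over two weeks, gives no rate, "and so will plan for enrollment of 15 participants".
- Section F adds that if discontinuation is higher than expected, "then we will consider additional enrollment as needed". It gives no number and no other trigger.

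Section IV.C (Study Design and Research Methods) sets the order of events. Consent is taken at the enrolment visit, and blood is then drawn for the metabolic panel, blood count and clotting tests. Only afterwards: "The research team will then follow-up the screening laboratory tests to determine final eligibility". Compliance is checked by a serum rifampin level at the second draw. The primary test is the paired Wilcoxon signed rank test.

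**The concern.** Enrolling 15 to obtain 15 compliant women works only if nobody is lost. The second draw can be missed, a woman can stop early, and the rifampin level can show non-compliance. If the 15 counts consented women, each laboratory failure is a further loss. The exclusions are broad enough to expect some: liver enzymes, creatinine, and any white cell, red cell, platelet or clotting value outside the reference range.

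The sentence on additional enrolment does not settle this. Read literally, it conflicts with the ceiling in Section IV.B. It is discretionary, and it responds only to discontinuation. Recruitment could stop at 15 while the number of usable pairs is smaller and the protocol still reports power for a number it did not reach.

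**Working it through.** **Inputs, all from Section F.** Mean ENG 137.4 pg/mL, SD 106.6, assumed pre/post correlation 0.875, target decrease 35%, alpha 0.05, power 0.9. Sidedness is not stated; two-sided is used below because it reproduces the plan's figure.

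**Step 1: reproduce the plan.**

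- SD of differences = √(2 × 106.6² × (1 − 0.875)) = 53.3.
- Target decrease = 0.35 × 137.4 = 48.1.
- Normal approximation: n = [53.3 × (1.960 + 1.282) / 48.1]² = 12.9, so 13. One-sided, the same formula gives 10.5, so 11.

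The plan's 13 is therefore the two-sided normal-approximation figure.

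**Step 2: power by number of pairs.** The standardised effect is 48.1/53.3 = 0.902.

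- Normal approximation: Φ(0.902√n − 1.960).
- Paired t-test: noncentral t with n − 1 degrees of freedom and noncentrality 0.902√n.
- Signed-rank test: simulation with normally distributed differences and the exact null distribution.

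| Pairs | Normal approximation | Paired t | Signed-rank (simulated) |
|---|---|---|---|
| 15 | 0.94 | 0.90 | 0.89 |
| 14 | 0.92 | 0.88 | 0.86 |
| 13 | 0.90 | 0.85 | 0.83 |
| 12 | 0.88 | 0.81 | 0.77 |

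The paired t-test first reaches 0.90 at 15 pairs. The signed-rank test reaches about 0.90 at 16. At this size the normal approximation is optimistic because it ignores estimation of the SD.

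**Step 3: what enrolling 15 delivers.** The documents give no loss rate. For illustration only, let d be an assumed combined loss, independent between women. It covers drop-out, missed draw and non-compliance, plus laboratory failure if the 15 counts consents. Expected pairs are 15(1 − d), and the chance that all 15 are usable is (1 − d)¹⁵.

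| Assumed loss d | Expected pairs | Chance of 15 pairs | Chance of at least 13 |
|---|---|---|---|
| 5% | 14.25 | 0.46 | 0.96 |
| 10% | 13.5 | 0.21 | 0.82 |
| 20% | 12.0 | 0.04 | 0.40 |

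**Step 4: the passages side by side.** Section IV.B fixes at most 15. Section F plans 15 compliant from 15 enrolled, then allows for more than 15. These agree only if there is no loss, or if the 15 in Section IV.B means something other than the enrolled number in Section F. Neither section says which.

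**The case against.** The strongest reply is that the plan ties 0.9 power to 13 women, so 15 leaves two to spare. By the plan's own normal approximation this is right: power is still 0.90 after two losses. But Section F adds those two women because ENG is non-normal, not as a reserve for drop-out. By the paired t-test or the planned signed-rank test, 13 pairs give 0.85 or about 0.83.

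Second, the 15 may mean women who have passed the laboratory tests, since Section IV.B lists those tests among its criteria. That reading is open. It removes laboratory failures from the count, but not drop-outs, missed draws or non-compliance.

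Third, Section F already foresees additional enrolment. This stands in part, and it is why the fix builds on that sentence.

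Fourth, 35% is a minimum. The Background reports a 61% median fall with carbamazepine. If the mean fall with rifampin were that large and the SD of differences stayed at 53.3 (both assumptions), the standardised effect would be 0.61 × 137.4 / 53.3 = 1.57, and even 11 pairs would give paired-t power above 0.99. The trial may well detect an effect with fewer pairs. The stated power, however, is for 35%.

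A reader might go further and infer that enrolment is capped at 15 consented women and that 0.9 power will not be delivered. The documents do not support this. They do not say that the 15 counts consents, they allow for additional enrolment, and they give no loss rate from which a shortfall could be established.

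**Conclusion.** The point holds as an inconsistency and an overstated figure. The ceiling in Section IV.B, the equal enrolled and compliant numbers in Section F, and the additional enrolment in Section F do not agree, and what the 15 counts is undefined. Fifteen compliant pairs are planned but not assured.

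The statement that 13 women give 0.9 power holds only under the normal approximation. For the planned test, 13 pairs give about 0.83 and 15 about 0.89, so there is no real reserve for loss, and each lost pair costs roughly 0.02 to 0.06 over the range shown.

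These figures rest on the plan's own SD and correlation and on a two-sided test. The signed-rank values also assume normal differences and would change with skew. A shortfall is a risk whose size depends on a loss rate that the documents do not give.

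**What to change.** 1. In Section F, replace the statement that 13 women give 0.9 power with power by number of analysable pairs for the signed-rank test (for example 15, 14, 13 and 12 pairs). State the sidedness and the assumed distribution of the differences.
2. Make Sections IV.B and F agree on what 15 counts. Preferably, it counts laboratory-eligible women who start rifampin, and the ceiling is reworded to match. Otherwise, state that it is a ceiling on consents and give the power at the smaller number of pairs expected, with the loss rate labelled as an assumption.
3. Let the additional enrolment in Section F also cover laboratory failures and missing pairs, and say whether women judged non-compliant are replaced. Decide this before the ENG batch assay. Section IV.C ships samples only when enrolment has ended, so replacement need not be influenced by ENG results.

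The cost is a slightly less favourable stated power and possibly a few more consents. At an assumed 10% loss, 15 / 0.9 = 16.7, so 17 women would be needed for 15 pairs; at 20%, 15 / 0.8 = 18.75, so 19.

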### **C. Study Design and Research Methods**

We propose a prospective, pre and post study to evaluate the pharmacokinetic effect of rifampin on serum ENG levels in contraceptive implant users. We will enroll healthy women using an ENG implant for at least 12 months and no greater than 36 months. Our exclusion and inclusion criteria are detailed as above. Interested participants will undergo a phone screening prior to scheduling an enrollment visit. At the enrollment visit, potential participants will have their vital signs checked in the form of a pulse and blood pressure and will have their height and weight measured for purposes of calculating a body mass index. We will review each potential participants past medical history and current medications to ensure study eligibility. If interested participants meet our non-laboratory inclusion and exclusion criteria, then they will undergo informed consent in a private clinic room.

After the participant has been consented, we will perform a blood draw to obtain whole blood and serum. Appropriate blood samples will be sent to the University of Colorado Clinical Laboratory for a comprehensive metabolic panel, complete blood count, and coagulation factor testing (PT/INR, PTT). We will also obtain additional blood tubes for measurement of serum estradiol and progesterone. These tubes will be sent to the UCH Clinical Laboratory for analysis if the participant's screening laboratory testing is normal. A blood sample for serum will be centrifuged on location and the serum collected for

storage in our -80°F freezer. For participants that meet our laboratory exclusion criteria, we will ultimately measure a serum baseline ENG concentration from the serum collected at the enrollment visit. The research team will then follow-up the screening laboratory tests to determine final eligibility based on the criteria discussed above. Eligible participants will then be given the options of either returning to our clinic to pick up the study medication or have the study medication mailed to them via FedEx.

Participants will then begin a 2 week regimen of rifampin at 600mg per day. This dose is the recommended dose for treatment of LTBI and duration of 2 weeks will achieve steady state rifampin levels with adequate time for liver enzyme induction. All participants will then return at the end of the second week for a repeat blood draw. We will again obtain serum as described above for planned measurement of serum ENG concentrations. We also obtain blood samples for repeat measurements of serum estradiol and progesterone. We will also measure a serum rifampin level at the time of the second ENG blood draw to confirm compliance. Serum estradiol, serum progesterone, and serum rifampin levels will all be measured at the UCH Clinical Laboratory. At the conclusion of enrollment, all stored serum samples will be de-identified and shipped to a Merck® laboratory for serum ENG concentration measurement. Batch analysis will be performed using a liquid chromatography mass-spectrometry method that has been previously validated. Participants will serve as their own controls for this study.

All participants will be required to use either a back-up non-hormonal method of birth control or abstain from intercourse during the study and for 2 weeks after the last dose of rifampin. Rifampin has a half-life of 3-4 hours, and thus, will be eliminated within 1-2 days of the last dose, but we will allow a full 2 weeks of buffer to ensure that the contraceptive effect of the implant has reinitiated before recommending resuming unprotected intercourse.

All study visits will occur at the Comprehensive Women's Health Clinic in Lowry. This is our Family Planning site for both clinical and research visits. All consent and enrollment processes will be conducted in a private clinic room and interested participants will be allowed as much time as needed to review the consent and ask any questions regarding the consent and study procedure.

#### **F. Data Analysis Plan:**

For this study, we aim to show a decrease in serum ENG concentrations of at least 35% from baseline, which would be consistent with the effect of a moderate to strong CYP3A4 inducer based on FDA standard definitions. Based on our previous cohort of 350 ENG implant users, we converted the median and range of serum ENG from that cohort to a mean of 137.4pg/mL with a SD of 106.6 based on Hozo et al's (BMC Med Res Methodol, 2005) formula. We then determined the assumed standard deviation of the differences in serum ENG concentrations to be 53.3 for before and after rifampin exposure based on an assumed correlation of 0.875 between these measurements. In order to find at least a 35% decrease in serum ENG concentrations (at least 48.1pg/mL decrease) with alpha level of 0.05 and power of 0.9, we will need 13 study compliant participants. Given the non-normal distribution of serum ENG concentrations, we will plan for 15 study compliant participants. We expect the discontinuation rate to be low given the short period

of treatment time (2 weeks), and so will plan for enrollment of 15 participants. If our discontinuation rate is higher than expected, then we will consider additional enrollment as needed.

We will use a paired Wilcoxon signed rank test to compare pre and post exposure serum ENG concentrations with each participant serving as their own control. We use the same analytic test for comparing pre and post exposure estradiol and progesterone levels. We will use a p-value of <0.05 as a cut-off for statistical significance. As each participant serves as her own control, we do not need to incorporate demographic factors into our analyses.

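### The plan ties power 0.9 to 13 participants without stating sidedness or sizing test; read as two-sided, 13 pairs give about 83–85% and the planned 15 about 88–90%

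*Combined protocol and SAP*

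**What the plan says.** All of the sizing is in section F, Data Analysis Plan. The plan converts an earlier cohort's median and range "to a mean of 137.4pg/mL with a SD of 106.6", assumes a correlation of 0.875 between the two measurements, and arrives at an SD of differences of 53.3. For a decrease of 48.1 pg/mL (35% of the mean) it states that "with alpha level of 0.05 and power of 0.9, we will need 13 study compliant participants". The next sentence raises the target: "Given the non-normal distribution of serum ENG concentrations, we will plan for 15 study compliant participants". Enrolment is also set at 15, with more enrolment to be considered if drop-out exceeds expectation.

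For the analysis, "We will use a paired Wilcoxon signed rank test to compare pre and post exposure serum ENG concentrations", and "We will use a p-value of <0.05 as a cut-off for statistical significance". The same test is planned for estradiol and progesterone. Neither the sizing nor the analysis text says whether the test is one- or two-sided, and the method that produced 13 is not named. No power is given for 15.

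The stated goal is directional: section F says "we aim to show a decrease in serum ENG concentrations of at least 35% from baseline", and the Hypothesis in section I refers to "etonogestrel concentrations at least 35% decreased from baseline measurements".

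**The concern.** The power statement is the plan's only one, and it belongs to a number that the trial does not use. A normal-approximation formula treats the SD as known. At about a dozen pairs that flatters the power of a paired t-test, and of a signed-rank test more so. If 13 came from that formula, the 0.9 attached to it is too high for the planned test.

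The two participants added for non-normality would then do a different job from the one described. They would make good the small-sample shortfall and leave little or nothing for non-normality. At stake is whether a reader can verify the stated power and knows what margin the 15 contains. The feasibility of the trial is not at stake.

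**Working it through.** **Inputs, all from section F:** mean 137.4 pg/mL, SD 106.6, correlation 0.875, alpha 0.05, power 0.9, planned number 15, planned test signed-rank. Sidedness is not given, so both cases are shown.

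**1. The plan's intermediate figures reproduce.**
- Decrease: 0.35 × 137.4 = 48.09, stated as 48.1.
- SD of differences: 106.6 × √(2 × (1 − 0.875)) = 106.6 × 0.5 = 53.3.
- Standardised effect: 48.1 / 53.3 = 0.902.

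**2. Where 13 could come from.** The normal formula is n = (z for alpha + z for power)² × (53.3/48.1)².
- Two-sided: (1.960 + 1.282)² × (53.3/48.1)² = 12.90, rounded up to 13.
- One-sided: (1.645 + 1.282)² × (53.3/48.1)² = 10.52, rounded up to 11.

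The two-sided normal formula therefore gives the stated 13. So do two one-sided small-sample calculations: 13 is the smallest n reaching 90% with a one-sided paired t-test (89.99% at 12) and with a one-sided signed-rank test (87.8% at 12). The documents do not settle which was used.

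**3. Power with small-sample methods, normal differences.** The paired t-test uses the noncentral t distribution with n − 1 degrees of freedom and noncentrality 0.902 × √n (3.25 at n = 13, 3.50 at n = 15). The signed-rank test uses exact critical values and 2,000,000 simulated trials per n (Monte Carlo standard error about 0.0002).

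| Pairs | Two-sided t | Two-sided signed-rank | One-sided t | One-sided signed-rank |
|---|---|---|---|---|
| 13 | 84.7% | 82.8% | 92.2% | 90.6% |
| 15 | 90.1% | 88.5% | 95.3% | 94.1% |

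Two-sided, 90% needs 15 pairs by paired t (87.7% at 14). By signed-rank it needs 16 to 17 pairs (89.99% at 16, 91.9% at 17). The attained two-sided alpha of the signed-rank test is 0.0479 at both 13 and 15.

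**4. What the step from 13 to 15 buys on the two-sided reading.** A paired t-test on perfectly normal differences already needs 15 for 90%. The two extra participants are used up before any allowance for non-normality.

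**5. Sensitivity to shape, two-sided signed-rank.** Both shapes are assumptions of this review, not of the plan.
- Lognormal levels with a proportional 35% fall: 98.3% at 13 and 99.3% at 15. The SD of differences in this case is 106.6 × √(1 + 0.65² − 2 × 0.875 × 0.65) = 56.9, slightly above the plan's 53.3.
- Left-skewed exponential differences with mean 48.1 and SD 53.3: 80.3% at 13 and 85.4% at 15.

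So the power at 15 could plausibly lie on either side of 0.9, depending on a shape that the plan does not specify.

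**The case against.** The case on the other side is substantial, and most of it stands.

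- **The 13 is not a calculation slip.** A reader might infer one from the gap between 0.9 and 83–85%. The documents do not support that, because every intermediate figure reproduces and 13 follows from a recognised formula. The fault lies in relying on a large-sample formula at this size, if that is what was done.
- **The test may be one-sided.** The hypothesis and the aim speak of a decrease, and one-sided the 13 does deliver 0.9 for both tests. This cannot be excluded. Two-sided remains the more natural reading: the significance cut-off is unqualified, the test is described as a comparison of before and after, and the same test is applied to estradiol and progesterone, for which no direction is stated.
- **The shortfall depends on normal differences, which the plan itself doubts.** Under lognormal levels with a proportional fall, 13 would be ample. That is a fair limit on the claim, though an unfavourable skew is equally undocumented.
- **The working target is 15, not 13.** At 15 the two-sided figures are within about 1.5 points of 0.9. That gap is small beside the uncertainty in an assumed correlation and in a mean and SD converted from a median and range. A reader might infer that the trial is underpowered or should be larger; the figures do not support that.

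One further inference should be blocked. The aim of showing at least a 35% decrease, placed beside the power figure, might suggest 90% power to demonstrate a fall of that size. The calculation and the planned signed-rank comparison address rejection of no change when the true mean decrease is 48.1 pg/mL.

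**Conclusion.** The point holds as a minor, conditional correction to the stated justification. On the ordinary two-sided reading with normal differences and SD 53.3, the number to which the plan attaches 0.9 falls short by about 5 points for a paired t-test (84.7%) and about 7 points for the planned test (82.8%). The trial's actual target of 15 gives 90.1% and 88.5%. On that reading the extra two participants cover the small-sample correction rather than non-normality. If the test is one-sided, 13 meets 0.9 and 15 exceeds it.

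On either reading the text is incomplete: sidedness and sizing method are missing, and no power is stated for the number that will be used. Enrolment equals the evaluable target, so if two participants were lost and not replaced, the two-sided power of the planned test would be the 82.8% shown for 13.

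**What to change.** Replace the statement linking 13 participants to power 0.9 with the sidedness and the power of the planned test at 15 evaluable pairs. Choose one version, and use the same sidedness in the analysis text.

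Two-sided:

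> With 15 evaluable pairs, the two-sided Wilcoxon signed-rank test at the 0.05 level has about 88% power (paired t-test: 90%) to reject no change if the true mean decrease is 48.1 pg/mL, assuming normally distributed differences with SD 53.3.

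One-sided, if that was intended for both sizing and analysis:

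> With 15 evaluable pairs, the one-sided Wilcoxon signed-rank test at the 0.05 level has about 94% power (paired t-test: 95%) under the same assumptions.

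In either case, add that skewed differences could raise or lower the figure, and that it is not the power to show a decrease of at least 35%. In the two-sided version, also drop the description of the two extra participants as an allowance for non-normality.

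The cost is protocol wording only. No participants or procedures are added. On the two-sided reading the stated power becomes slightly less favourable, about 88% instead of 90%.
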